## 8.2 Dose Modifications for Binimetinib

CTCAE System/Organ/Class (SOC)	ADVERSE EVENT	Grade	ACTION FOR BINIMETINIB C
Cardiac disorders	Left ventricular systolic dysfunction	Grade 1-2 Asymptomatic absolute decrease of >10% compared to baseline and below institutional LLN	Hold binimetinib and repeat evaluation of LVEF within 2 weeks: 
 
○ If the LVEF recovers (defined as LVEF <math>\geq</math>50% or <math>\geq</math>LLN and absolute decrease <math>\leq</math>10% compared to Baseline) in <math>\leq</math>21 days, reduce 1 dose level after approval of the Principal Investigator. Monitor LVEF 2 weeks after resuming binimetinib, every 4 weeks for 12 weeks and subsequently as per protocol
 
○ If the LVEF does not recover in <math>\leq</math>21 days, permanently discontinue binimetinib. Closely monitor LVEF until resolution or for up to 16 weeks
 
 No dose re-escalation allowed after dose reduction for LVEF
Eye disorders a,b	Retinal detachment	Grade 1	Maintain dose level of binimetinib and increase frequency of ophthalmic monitoring to at least every 14 days until stabilization or resolution
		Grade 2	Maintain dose level of binimetinib and refer the patient to ophthalmologist within 1 week: 
 
○ If resolved to Grade <math>\leq</math>1 in <math>\leq</math>21 days, maintain dose of binimetinib
 
○ If not resolved to Grade <math>\leq</math>1 in <math>\leq</math>21 days, reduce 1 dose level of binimetinib or maintain dose of binimetinib based upon the Investigator's discretion after consultation with the ophthalmologist
 

		Grade 3	Hold binimetinib and refer the patient to ophthalmologist within 1 week: 
 
○ If resolved to Grade <math>\leq</math>1 in <math>\leq</math>21 days, reduce 1 dose level of binimetinib
 
○ If not resolved to Grade <math>\leq</math>1 in <math>\leq</math>21 days, permanently discontinue binimetinib and close follow-up with ophthalmic monitoring until stabilization or resolution
 

		Grade 4	Permanently discontinue binimetinib and immediate follow-up with ophthalmic monitoring until stabilization or resolution
	Retinal vascular disorder (RVO)	Any	Permanently discontinue binimetinib and immediate follow-up with ophthalmic monitoring until stabilization or resolution
	Eye disorders – Other specify – any non-retinal events	Grade 1-2	Maintain dose level of binimetinib and increase frequency of ophthalmic monitoring to at least every 14 days until stabilization or resolution

CTCAE System/Organ/Class (SOC)	ADVERSE EVENT	Grade	ACTION FOR BINIMETINIB C
Eye disorders a,b	Eye disorders – Other specify – any non-retinal events	Grade 3	
Hold binimetonib and refer patient to ophthalmologist within 1 week:
 
 
○ If resolved to Grade <math>\leq 1</math> in <math>\leq 21</math> days, reduce 1 dose level of binimetonib
 
○ If not resolved to Grade <math>\leq 1</math> in <math>\leq 21</math> days, permanently discontinue binimetonib and close follow-up with ophthalmic monitoring until stabilization or resolution
 

		Grade 4	Permanently discontinue binimetonib and immediate follow-up with ophthalmic monitoring until stabilization or resolution
Gastrointestinal disorders	Diarrhea	Grade 1-2 Uncomplicated	
Consider temporary hold of binimetonib until resolved to Grade <math>\leq 1</math>
 
Resume binimetonib at current dose level

		Grade 1-2 Complicated	
Temporarily hold binimetonib until resolved to Grade <math>\leq 1</math>
 
Resume binimetonib at 1 reduced dose level

		Grade 3	
Temporarily hold binimetonib until resolved to Grade <math>\leq 1</math>
 
Resume binimetonib at 1 reduced dose level

		Grade 4	
Temporarily hold binimetonib until resolved to Grade <math>\leq 1</math>
 
Resume binimetonib at 1 reduced dose level

Investigations	Alanine aminotransferase increased (ALT) OR Aspartate aminotransferase increased (AST)	Grade 1	Maintain dose level of binimetonib
	Alanine aminotransferase increased (ALT) OR Aspartate aminotransferase increased (AST) AND Blood bilirubin increased	Grade 2 For patients with Baseline ALT/AST values <math>\leq</math>ULN: ALT or AST $>3.0$ to $5.0 \times$ ULN and blood bilirubin (total) $\leq 2.0 \times$ ULN	
Hold binimetonib until resolved to Grade <math>\leq 1</math>, then:
 
 
○ If resolved in <math>\leq 14</math> days, maintain dose level of binimetonib
 
○ If not resolved in <math>\leq 14</math> days, reduce 1 dose level of binimetonib
 

CTCAE System/Organ/Class (SOC)	ADVERSE EVENT	Grade	ACTION FOR BINIMETINIB C
Investigations	Alanine aminotransferase increased (ALT) OR Aspartate aminotransferase increased (AST) AND Blood bilirubin increased	Grade 2 For patients with liver metastases or ALT/AST Baseline values >ULN: ALT or AST 3 × Baseline value to 5.0 × ULN and blood bilirubin (total) ≤2.0 × ULN	Hold binimetinib until resolved to Grade ≤2, then: ○ If resolved in ≤14 days, maintain dose level of binimetinib ○ If not resolved in ≤14 days, reduce 1 dose level of binimetinib
	Grade 2 For all patients: ALT or AST >3.0 to 5.0 × ULN and blood bilirubin (total) >2.0 × ULN	Hold binimetinib until resolved to Grade ≤1, then: ○ If resolved in ≤7 days, reduce 1 dose level of binimetinib ○ If not resolved in ≤7 days, permanently discontinue binimetinib	
	Grade 3 ALT or AST >5.0 to 8.0 × ULN and blood bilirubin (total) ≤2.0 × ULN	Hold binimetinib until resolved to Grade ≤1 (Grade ≤2 in case of liver metastases) then: ○ If resolved in ≤14 days, maintain dose level of binimetinib ○ If not resolved in ≤14 days, reduce 1 dose level of binimetinib	
	Grade 3 ALT or AST >8.0 × ULN and blood bilirubin (total) ≤2.0 × ULN	Permanently discontinue binimetinib	

CTCAE System/Organ/Class (SOC)	ADVERSE EVENT	Grade	ACTION FOR BINIMETINIB C
Investigations	Alanine aminotransferase increased (ALT) OR Aspartate aminotransferase increased (AST) AND Blood bilirubin increased	Grade 3 ALT or AST $>5.0 \times$ ULN and blood bilirubin (total) $>2.0 \times$ ULN	Permanently discontinue binimetinib
	Alanine aminotransferase increased (ALT) OR Aspartate aminotransferase increased (AST)	Grade 4 $>20.0 \times$ ULN	Permanently discontinue binimetinib
	CPK increased	Grade 1-2	Maintain dose level of binimetinib 
 
○ If total CK <math>\geq 3 \times</math> ULN, measure CK, CK isoenzymes and myoglobin in blood or urine weekly for 3 weeks and if total CK remains <math>\leq</math> Grade 2, continue to assess CK, CK isoenzymes and myoglobin along with regularly scheduled clinical chemistry assessments
 

		Grade 3 $>5.0$ to $10.0 \times$ ULN	If asymptomatic, maintain dose of binimetinib and monitor closely 
 
○ Measure CK, CK isoenzymes and myoglobin in blood or urine weekly for 3 weeks and if total CK remains <math>\leq</math> Grade 3, continue to assess CK, CK isoenzymes and myoglobin along with regularly scheduled clinical chemistry assessments
 
 If symptomatic (muscle pain/spasms), interrupt binimetinib until resolved to Grade $\leq 1$ and monitor closely, then: 
 
○ If resolved in <math>\leq 21</math> days, reduce 1 dose level of binimetinib
 
○ If not resolved in <math>\leq 21</math> days, permanently discontinue binimetinib
 

CTCAE System/Organ/Class (SOC)	ADVERSE EVENT	Grade	ACTION FOR BINIMETINIB C
Investigations	CPK increased	Grade 4	
If asymptomatic, interrupt binimetonib until resolved to Grade <math>\leq 1</math> and monitor closely, then:
 
 
o If resolved in <math>\leq 21</math> days, reduce 1 dose level of binimetonib
 
o If not resolved in <math>\leq 21</math> days, permanently discontinue binimetonib
 
 
If symptomatic, permanently discontinue binimetonib

	Electrocardiogram QT corrected interval prolonged	Grade 3 mean triplicate QTcF $\geq 501$ msec (confirmed by a separate mean triplicate ECG)	
First Occurrence:
 
 
o Interrupt binimetonib. Electrolyte abnormalities (if applicable) should be corrected and any concomitant medication that could potentially prolong QT should be discontinued
 
o Monitor patient until resolution of the AE. Include a consultation with a cardiologist, if indicated
 
o Once resolved to Grade <math>\leq 1</math>, resume binimetonib at 1 reduced dose level
 
 
Second Occurrence:
 
 
o If second occurrence is attributed to binimetonib, permanently discontinue binimetonib
 
 
No dose re-escalation after dose reduction due to QTcF<math>>500</math>msec

Skin and subcutaneous tissue disorders	Rash acneiform or Rash maculo-papular	Grade 1	
Maintain dose level of binimetonib
 
Initiate Initial Rash Treatment Regimen (Section 9.9f) if it was not already started and rash should be closely monitored

		Grade 2	
First Occurrence:
 
 
o Maintain dose level of binimetonib and rash should be closely monitored
 
o Initiate Initial Rash Treatment if it was not already started
 
o Reassess within <math>\leq 14</math> days. If rash worsens or does not improve, interrupt binimetonib until resolved to Grade <math>\leq 1</math>. Resume binimetonib at current dose level
 
 
Second Occurrence:
 
 
o Reassess within <math>\leq 14</math> days. If rash worsens or does not improve, interrupt binimetonib until resolved to Grade <math>\leq 1</math>. Resume binimetonib at 1 reduced dose level
 

CTCAE System/Organ/Class (SOC)	ADVERSE EVENT	Grade	ACTION FOR BINIMETINIB c
Skin and subcutaneous tissue disorders	Rash acneiform or Rash maculo-papular	Grade 3	First Occurrence: 
 
○ Interrupt binimetonib until resolved to Grade <math>\leq 1</math> Reassess weekly; Resume binimetonib at current dose level
 
○ Consider referral to dermatologist and manage rash per dermatologist's recommendation
 
 Second Occurrence: 
 
○ Interrupt binimetonib until resolved to Grade <math>\leq 1</math> Reassess weekly; Resume binimetonib at 1 reduced dose level
 
○ Consider referral to dermatologist and manage rash per dermatologist's recommendation
 

		Grade 4	Permanently discontinue binimetonib
Vascular disorders	Thromboembolic event	Grade 3	Withhold binimetonib for up to 3 weeks. 
 
• If improved to Grade 0 or 1, resume at reduced dose.
 
• If not improved, permanently discontinue
 

		Grade 4	Permanently discontinue binimetonib
All other events	Related to binimetonib treatment	Grade 1-2	
 
• If the event is Grade 1 or non-persistent Grade 2, maintain dose level of binimetonib and monitor until stabilization or resolution
 
• If the event is a persistent Grade 2 AE not responsive to a specific therapy, consider binimetonib dose interruption or reduction
 

		Grade 3	Interrupt binimetonib until resolved to $\leq$ Grade 1 or to pretreatment/Baseline level If the event resolves $\leq 21$ days, then binimetonib may be resumed at 1 reduced dose level based upon the Investigator's discretion
		Grade 4	Permanently discontinue binimetonib

a Further evaluation with specialized retinal imaging (e.g., OCT [spectral domain OCT recommended] of the macula for non-vascular abnormalities; and color fundus photography of the central 30 degrees and/or fluorescein angiography for vascular abnormalities) is recommended.

b Images/results of the ophthalmic examinations (at a minimum, OCT, color fundus photography and/or fluorescein angiography) must be made available upon Sponsor request.

c If binimetonib is discontinued, patient can continue on single-agent pembrolizumab.

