#### 4.0 Study Calendar

##### 4.1 Test Schedule for Breast Cancer

Tests and procedures			Active Treatment									End of Treatment	Post-Treatment
	$\leq 28$ days prior to registration	$\leq 14$ days prior to registration	Pre-Tx biopsy	Cycle 1 binimetinib alone	Cycles 2-3 with pembrolizumab		Cycles 4-8	Cycle 9	Cycle 10 and beyond	At time of disease progression	Safety follow up: 30 days post-discontinuation		
					Prior to C2 D1	Prior to C3 D1	Prior to Day 1	Prior to Day 1					
Window					$\pm 3$ days	$\pm 3$ days	$\pm 3$ days	$\pm 3$ days	$\pm 3$ days	$\pm 7$ days		$\pm 7$ days	
Clinical Procedures													
History and exam  , vital signs (temp, BP, heart rate), weight, ECOG PS	X				X	X	X	X	X	X		X	
Height	X												
Concomitant medications	X				X	X	X	X	X			X	
Pregnancy test 		X 											
Hematology: CBC/diff with PLT		X			X	X	X	X	X			X	
Chemistry Panel 		X			X	X	X	X	X			X	
CA15-3		X			X	X	X	X	X			X	
Creatine Kinase (CK/CPK), troponin T 4,R		X			X	X	X	X	X			X	
Urinalysis		X			X	X	X	X	X			X	
Coagulation INR (PT), PTT		X											
Total T3, Free T4, TSH R		X			X	X	X	X	X			X	
Tumor measurement by CT or MRI 	X						X						
Bone scan (only if clinically indicated)	X												

\*Retreatment Phase-Patients entering the study for retreatment will follow the test and procedures as indicated in the study calendar for Cycle 2 and beyond. Labs and blood forms are not required to be entered into RAVE during the Retreatment Phase.

 All tests and procedures are clinically indicated, unless noted with an R to indicate funding by research

 For women of childbearing potential only: Serum  $\beta$ HCG must be done  $\leq 7$  days prior to registration, and if necessary, again  $\leq 72$  hours prior to Cycle 1, Day 1

 AST (SGOT), ALT (SGPT), alkaline phosphatase, total bilirubin (direct if TBili is elevated), BUN, creatinine with calculated creatinine clearance, albumin, total protein, uric acid, bicarbonate, calcium, chloride, glucose, LDH, magnesium, phosphorus, potassium, sodium

 Follow up for total creatine kinase (CK/CPK)  $\geq 3$  X ULN will include weekly assessment of isoenzymes and myoglobin in blood/or urine, and troponin T as applicable

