## 8.0 Dosage Modification Based on Adverse Events

Strictly follow the modifications in this table for the first **two** cycles, until individual treatment tolerance can be ascertained. Thereafter, these modifications should be regarded as guidelines to produce mild-to-moderate, but not debilitating, side effects. If multiple adverse events are seen, administer dose based on greatest reduction required for any single adverse event observed. Reductions or increases apply to treatment given in the preceding cycle and are based on adverse events observed since the prior dose.

→**ALERT:** *ADR reporting may be required for some adverse events (See Section 10.0)←*

\*\* Use the following to describe actions in the Action column:

- Omit = Treatment is not given for this cycle
- Hold/Delay = Treatment can be made up as part of this cycle
- Discontinue = Treatment is totally stopped

**NOTE:** If the patient experiences a significant adverse event requiring a dose reduction at the start of the next cycle, then the dose will remain lowered.

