Please refer to the table below for dose adjustment recommendations for binimatinib-induced adverse events.

For adverse events that can be attributed to either pembrolizumab or binimatinib, dose adjustment for both agents will be applied. These toxicities include but are not limited to diarrhea and liver function abnormalities.

→ → *Use the NCI Common Terminology Criteria for Adverse Events (CTCAE) current version 4.0\**  
*unless otherwise specified ← ←*

\* Located at [http://ctep.cancer.gov/protocolDevelopment/electronic\\_applications.ctc.htm](http://ctep.cancer.gov/protocolDevelopment/electronic_applications.ctc.htm)

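### The Grade 2 ALT/AST row for liver metastases or raised baseline holds binimetinib until Grade ≤2, which every triggering value already meets

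*Combined protocol and SAP*

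**What the plan says.** Section 8.2 gives three Grade 2 rows for raised ALT or AST.

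- **Normal baseline.** The row introduced by "For patients with Baseline ALT/AST values" at or below ULN covers >3.0 to 5.0 × ULN with bilirubin at most 2.0 × ULN. Its action is "Hold binimetinib until resolved to Grade ≤1, then" keep the dose if that took 14 days or less, and otherwise go down one level.
- **Liver metastases or baseline above ULN.** The trigger is "ALT or AST 3 × Baseline value to 5.0 × ULN and blood bilirubin (total) ≤2.0 × ULN". The action is "Hold binimetinib until resolved to Grade ≤2, then" the same 14-day test.
- **All patients, bilirubin above 2.0 × ULN.** This row covers >3.0 to 5.0 × ULN and also releases at Grade ≤1.

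The next row, Grade 3 at >5.0 to 8.0 × ULN with bilirubin at most 2.0 × ULN, reads "Hold binimetinib until resolved to Grade ≤1 (Grade ≤2 in case of liver metastases) then" and again applies a 14-day test.

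On the force of the table, Section 8.0 says "Strictly follow the modifications in this table for the first" two cycles; after that it is guidance. Section 8.1 adjusts both agents for events attributable to either: "These toxicities include but are not limited to diarrhea and liver function abnormalities".

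**The concern.** A hold needs a release condition that is not yet met when the hold begins. In the liver-metastasis/raised-baseline row, the label and the release name the same grade, so the patient qualifies to resume at the moment of stopping. The 14-day clock then has nothing to measure.

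This looks like a drafting slip. Where the table intends no interruption, as for Grade 1 ALT/AST, it says to maintain the dose. This row instead prescribes a hold, a clock and a possible reduction.

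The row covers patients who start with liver disease or abnormal enzymes. Section 15.17 lists raised AST and ALT as very common with binimetinib (at least 10%) and acute hepatic failure as uncommon. During the two strict cycles, a site that follows the row exactly does nothing. In Cycle 1 the patient receives binimetinib alone for 14 days (Sections 7.11 and 7.13), so no pembrolizumab rule is yet in play. The "Chemistry Panel" in Section 4.1 is scheduled on treatment before Cycle 2 Day 1 and again before Cycle 3 Day 1, so those results are natural points at which the row would be applied.

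**Working it through.** The plan states no figure to reproduce; this is a logic check on a dose rule. Let *b* be the baseline and *v* the on-treatment ALT or AST, both in multiples of ULN, with bilirubin at most 2.0 × ULN.

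**Inputs.** From Section 8.2, Grade 2 is *v* >3.0 to 5.0 and Grade 3 begins at *v* >5.0. Hence Grade ≤2 means *v* ≤ 5.0, and Grade ≤1 means *v* ≤ 3.0. From Section 3.18, entry allows *b* up to 2.5, or up to 5 with liver metastases.

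**Step 1: trigger against release.** The row triggers when 3*b* ≤ *v* ≤ 5.0 and releases when *v* ≤ 5.0. The upper limit of the trigger is the release limit, so every triggering value is already released, whatever *b* is. The row's own label gives the same answer without numbers: an event graded 2 is Grade ≤2.

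**Step 2: the 14-day branch.** Time to release is zero days, so the branch for more than 14 days is never entered from within the row. If *v* rises above 5.0, the Grade 3 rows govern instead.

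**Step 3: where the row exists.** It contains values only if 3*b* ≤ 5.0, that is *b* ≤ 5/3 = 1.67.
- *b* = 1.2: 3 × 1.2 = 3.6, so 3.6 to 5.0.
- *b* = 1.5: 3 × 1.5 = 4.5, so 4.5 to 5.0.
- *b* = 2.0: 3 × 2.0 = 6.0, above 5.0, so empty.

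**Step 4: overlap.** Take liver metastases with *b* = 0.8 and *v* = 4.5. The normal-baseline row applies because *b* ≤ 1 and 3.0 < 4.5 ≤ 5.0. The liver-metastasis row also applies because 3 × 0.8 = 2.4 ≤ 4.5 ≤ 5.0. One releases at *v* ≤ 3.0, the other at *v* ≤ 5.0.

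**Step 5: one value, several patients (*v* = 4.5).**

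| Patient | Release now | Release after the fix |
|---|---|---|
| *b* = 0.8, no liver metastases | ≤3.0 | ≤3.0 |
| *b* = 0.8, liver metastases | ≤3.0 and ≤5.0 (conflict) | ≤3.0 |
| *b* = 1.2 | ≤5.0, met at once | ≤3.0 |
| *b* = 2.0 | no ALT/AST hold row | no ALT/AST hold row |

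**Step 6: does the fix work?** Set the lower bound to the greater of 3*b* and >3.0, and the release to *v* ≤ 3.0.
- For *b* ≤ 1.0, 3*b* ≤ 3.0, so the range is >3.0 to 5.0, identical to the normal-baseline row. The conflict disappears.
- For 1.0 < *b* ≤ 1.67, 3*b* > 3.0, so the range is 3*b* to 5.0.
- Every triggering value is then above 3.0, so none is released at trigger. The release is attainable, because *b* ≤ 1.67 lies below 3.0.

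**The case against.** **Other rules limit the harm.** This stands, and it sets the size of the point. Section 8.1 has adverse events followed weekly or as clinically appropriate. Once pembrolizumab has started, Table 8.31 holds it for drug-related Grade 2 ALT/AST until Grade 0-1. Section 9.9a adds more frequent liver tests and corticosteroids for Grade 2 hepatic events judged related to pembrolizumab. A reader might infer that liver toxicity in this subgroup goes unmanaged; the documents do not support that. None of these provisions, however, supplies a release grade for binimetinib.

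**The looser release may be deliberate.** The Grade 3 row does allow Grade ≤2 for liver metastases, which suggests some tolerance was wanted. There it requires real improvement, from above 5.0 to 5.0 or below. Copied into a Grade 2 row it requires none, and this row also takes in patients with raised baseline and no liver metastases, to whom the Grade 3 allowance does not extend. Tolerance may explain the wording, but it does not make the hold work.

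**Another release could be chosen.** Return to baseline is possible; the Grade 3 entry for all other events permits it. The choice is clinical. For the baselines this row reaches (*b* ≤ 1.67), Grade ≤1 is the less demanding of the two and matches the neighbouring rows.

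**Two further inferences do not hold.** With liver metastases and *b* = 0.5 the printed range starts at 3 × 0.5 = 1.5 × ULN, so a reader might infer that Grade 1 values trigger a hold. The row is labelled Grade 2, the Grade 1 row maintains the dose, and Section 8.1 generally advises against interrupting for Grade 1 events, so this is only loose drafting. A reader might also call the absence of a hold above *b* = 1.67 an error. Since entry allows up to 5 × ULN with liver metastases, tolerating values to 5.0 × ULN may be intended.

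**Conclusion.** The row is wrong as written: its release is met at trigger, its dose-reduction branch is unreachable from within the row, and it contradicts the normal-baseline row for liver-metastasis patients with baseline at or below ULN. This is an error of dose-rule logic, and it rests only on the table's own grade limits.

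The scale is minor: one row. The exposure is greatest in Cycle 1, when binimetinib is given alone, and later when the event is attributed to binimetinib alone. The practical change falls on baselines above 1.0 and up to 1.67 × ULN, plus the overlap group. The documents do not give the share of patients in this row, so no patient count is claimed.

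It would be too much to infer that the phase I dose finding is affected. The DLT definition for ALT/AST in Section 7.42 starts at Grade 3 and does not use this row. Sample size and analysis are likewise untouched.

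**What to change.** Change two cells of the row.

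1. Release: Grade ≤1 (≤3.0 × ULN), as in the other two Grade 2 rows.
2. Lower bound: the greater of 3 × baseline and >3.0 × ULN. This also removes the conflict with the normal-baseline row.

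When making the edit, ask the clinical team to confirm two matters that the documents do not settle.

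- **Fit with the Grade 3 row.** Its Grade ≤2 release for liver metastases is left unchanged here. A liver-metastasis patient caught by the corrected row at 4.9 × ULN would be held to ≤3.0, while one at 5.1 × ULN would be released at ≤5.0. The normal-baseline row already produces the same contrast today for liver-metastasis patients with baseline at or below ULN.
- **Baselines above 1.67 × ULN.** The row is empty there, so with bilirubin at most 2.0 × ULN no ALT/AST row holds binimetinib up to 5.0 × ULN. Confirm that this is intended.

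The clinical cost is slightly more or longer binimetinib holds in this subgroup. Eligibility, grade boundaries, the DLT definition, sample size and analysis do not change.

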## 7.413 Investigators are to contact the Study Chair as soon as any dose-limiting toxicity (DLT) occurs.

## 7.42 Definitions of DLT

## 7.421 For this protocol, DLT will be defined as follows for Cycle 2 only:

CTCAE SOC/AE*	Definition (CTCAE Grade)
Blood and lymphatic system disorders	Grade 4
• Febrile neutropenia	
Eye disorders	≥Grade 3
• Blurred vision	
• Flashing lights	
• Floaters	
Eye disorders	Grade 2 lasting >14 consecutive days confirmed by ophthalmic examination Or Grade 3
• Retinopathy	
Eye disorders	Any grade confirmed by ophthalmic examination
• Retinal vascular disorder	

CTCAE SOC/AE*	Definition (CTCAE Grade)
Eye disorders 
 
• Eye disorders, Other specify
 
	Any visual event $\geq$ Grade 3 confirmed by ophthalmic examination
Investigations 
 
• Alanine aminotransferase increased
 
 OR 
 
• Aspartate aminotransferase increased
 
	$\geq$ Grade 3
Investigations 
 
• Blood bilirubin increased
 
	$\geq$ Grade 3
Investigations 
 
• CPK increased
 
	$\geq$ Grade 3 associated with an increase in creatinine $\geq$ 1.5 times patient's baseline (screening) creatinine level
Investigations 
 
• Creatinine increased
 
	$\geq$ Grade 3
Investigations 
 
• Ejection fraction decreased
 
	$\geq$ Grade 3 Or Absolute decrease of LVEF $>$ 10% compared to Baseline and is below the institution's LLN
Investigations 
 
• Electrocardiogram QT corrected interval prolonged
 
	$\geq$ Grade 3 on at least two separate ECGs
Investigations 
 
• Neutrophil count decreased
 
	Grade 4 lasting $>$ 7 consecutive days
Investigations 
 
• Platelet count decreased
 
	Grade 3 with signs of clinically significant bleeding Or Grade 4
Gastrointestinal disorders 
 
• Diarrhea
 
	$\geq$ Grade 3 for $\geq$ 48 hours despite optimal anti-diarrheal therapy Or Grade 4
Gastrointestinal disorders 
 
• Nausea
 
• Vomiting
 
	Grade 3 for $\geq$ 48 hours despite optimal anti-emetic therapy Or Grade 4

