General disorders and administration site conditions 
 
• Fatigue
 
	Grade 3 lasting $>$ 14 consecutive days
Skin and subcutaneous tissue disorders 
 
• Rash maculo-papular
 
• Palmar-plantar erythrodysesthesia syndrome
 
• Photosensitivity
 
	Grade 3 lasting $>$ 14 consecutive days despite maximal skin toxicity treatment per local practice Or Grade 4
Vascular disorders 
 
• Hypertension
 
	Grade 3 lasting $>$ 14 consecutive days Or Grade 4
Other events**	Any $\geq$ Grade 3

\*Adverse event at least possibly related to the study medication.

\*\* Lymphocyte count decreased  $\geq$ Grade 3 (unless clinically significant) and Grade 3 alopecia will not be considered a DLT

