### 8.1 Dose Levels (Based on Adverse Events in Table 8.2)

Dose Level	Binimetinib
0*	45 mg BID
-1	30 mg BID
-2	15 mg BID
-3	Discontinue

\*Dose level 0 refers to the starting dose.

**NOTE:** If binimetinib is discontinued, the patient can continue treatment on single-agent pembrolizumab. The patient will continue to follow the test schedule (Section 4.1)

For binimetinib, if dose reduction goes below -2 dose level, then binimetinib must be discontinued. If binimetinib is started at -2 dose level, then there are no further dose reductions.

NOTE: There are no dose changes for pembrolizumab, only dose schedule modifications.

For patients who do not tolerate the 45 mg BID dosing schedule, dose adjustment to 30 mg BID is permitted in order to allow the patient to continue on study drug. The following guidelines need to be applied and these changes must be recorded on the specific section of the patient record.

A dose reduction below 15 mg BID is not allowed. Dose interruptions of more than 21 days are not allowed.

Missed/skipped doses will not be made up (i.e. the patient should not double their dose if the previous dose was missed). When the adverse event that resulted in a dose reduction improves to and remains stable at Grade 1 or less for a minimum of 21 days, the dose can be re-escalated at the investigators discretion provided there are no other concomitant adverse events.

No dose re-escalation is allowed after dose reduction due to left ventricular dysfunction or prolonged QTcF >500 msec.

Dose reduction/interruption/discontinuation decisions should be based on the CTCAE grade of the adverse event (AE) and the guidelines provided below. In general, doses should not be reduced or interrupted for Grade 1 events, but treatment to control symptoms should be provided as appropriate. All AEs should be followed weekly or as clinically appropriate until stabilization or resolution.

A patient with a Grade 4 AE may resume treatment at the lower dose level if the AE recovers to grade  $\leq 1$  within 21 days of interrupting drug and, if in the opinion of the Investigator and Medical Monitor, the event is not life-threatening, and the patient can be managed and monitored for recurrence of AE. Dose interruptions of more than 21 days are not allowed unless approved by the Investigator, and the Pfizer Inc. (formerly Array Biopharma LLC and Array Biopharma Inc.) Medical Monitor or designee.

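### The Grade 3 CPK row of Table 8.2 keeps an asymptomatic patient on binimetinib even when creatinine has risen to 1.5 times screening, a pair the DLT table treats as dose-limiting

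*Combined protocol and SAP*

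**What the plan says.** **Dosing table (Section 8.2, CPK increased, Grade 3).** There are two branches. Without symptoms: "If asymptomatic, maintain dose of binimetinib and monitor closely", with weekly CK, isoenzymes and myoglobin for three weeks. With symptoms: "If symptomatic (muscle pain/spasms), interrupt binimetinib until resolved to Grade" 1 or lower, then one dose level down if that takes no more than 21 days, otherwise permanent discontinuation.

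**DLT table (Section 7.421).** CPK of Grade 3 or higher is a Cycle 2 DLT when "associated with an increase in creatinine" of at least 1.5 times the screening value. The footnote adds the attribution condition: "Adverse event at least possibly related to the study medication". Symptoms are not required.

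**Creatinine in Table 8.2.** It has no row, so the row for all other events applies. "If the event is Grade 1 or non-persistent Grade 2, maintain dose level of binimetonib and monitor until stabilization or resolution". Next: "If the event is a persistent Grade 2 AE not responsive to a specific therapy, consider binimetonib dose interruption or reduction". Grade 3 is interrupted and Grade 4 discontinued, if related to binimetinib.

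**General rules.** Section 8.0 makes the table strict for the first two cycles and guidance afterwards; with several events, the dose follows the largest reduction that any one event requires. Section 8.1 adds: "In general, doses should not be reduced or interrupted for Grade 1 events".

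**The concern.** The DLT table uses creatinine to separate a dangerous Grade 3 CPK rise from a tolerable one. The dosing table for the same event drops that marker and sorts patients by muscle symptoms alone. A site that follows Table 8.2 would therefore continue the current binimetinib dose in a patient whose laboratory pair the protocol elsewhere calls dose-limiting. Section 15.199a warns of myositis and, rarely, rhabdomyolysis, and Section 15.17 lists raised CPK as very common and renal failure as uncommon with binimetinib. What is at stake is the safety of individual patients in both phases, since Table 8.2 is not restricted to Phase I.

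**Working it through.** The plan gives no figure to reproduce. The check applies the rules to one patient: related Grade 3 CPK, no muscle symptoms, and creatinine at or above 1.5 times screening.

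**Step 1: action on binimetinib by creatinine grade.** The documents do not print the CTCAE creatinine cut-offs, so the trace runs by grade.

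| Creatinine grade | CPK row | All other events row | Result under the Section 8.0 rule |
|---|---|---|---|
| 1 | maintain | maintain | maintain |
| 2, non-persistent | maintain | maintain | maintain |
| 2, persistent | maintain | consider | optional |
| 3, related | maintain | interrupt | interrupt |
| 4, related | maintain | discontinue | discontinue |

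The gap is the first two lines and, in part, the third. The multiple-event rule does not close it: where each event alone gives maintain, so does the pair. Symptomatic Grade 3 CPK and all Grade 4 CPK are already interrupted or discontinued.

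The 1.5 threshold can be met inside the normal range. With assumed values of 0.7 mg/dL at screening and an upper limit of 1.1 mg/dL, 1.5 × 0.7 = 1.05 mg/dL, which is below 1.1.

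**Step 2: the other DLT rows.** Section 7.421 has 19 rows. The Table 8.2 action at Grade 3 or higher, assuming the event is related to binimetinib where the catch-all row applies, is:

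- Discontinue: febrile neutropenia (Grade 4), retinal vascular disorder, neutrophils (Grade 4).
- Hold or interrupt, with discontinuation at higher grades or values where stated: blurred vision/flashing lights/floaters, retinopathy, other eye disorders, ALT/AST, bilirubin, creatinine, ejection fraction, QTc, platelets, diarrhea, nausea/vomiting, fatigue, rash/hand-foot/photosensitivity, hypertension, other events.
- Maintain possible: CPK with creatinine.

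That is 3 + 15 + 1 = 19, so 18 lead to a hold, interruption or discontinuation and 1 can return maintain. Below Grade 3 there is one other DLT criterion without a mandated hold: Grade 2 retinopathy lasting more than 14 days, whose nearest row (Grade 2 retinal detachment) keeps the dose.

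**Step 3: when the instruction binds.** Cycle 1 lasts 14 days and Cycle 2 lasts 21, so C2 D1 is day 15 and C3 D1 is day 36. Section 4.1 schedules chemistry before each.

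- Pair found before C2: it arises on binimetinib alone, so it is not a DLT, but maintain is a strict instruction.
- Pair arising in Cycle 2 and found on scheduled tests: seen before C3, when the table is guidance. The strict instruction applies within Cycle 2 only if creatinine is measured off schedule.

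**Step 4: detection.** The gap between scheduled creatinine values is 36 − 15 = 21 days. With ±3 days at each visit it is 33 − 18 = 15 to 39 − 12 = 27 days. If CK triggers weekly checks at day 15, they fall on about days 22, 29 and 36, and only day 36 coincides with a chemistry panel. Neither the CPK rows nor footnote 4 of Section 4.1 names creatinine among the weekly tests.

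**The case against.** The strongest reply is that the two tables do different jobs: the DLT definition drives cohort and MTD decisions, while Table 8.2 manages individual patients. That stands. The retinopathy example shows that a DLT need not lead to a hold, so a reader who infers an outright contradiction goes too far. The Grade 1 rule in Section 8.1 also explains the action for creatinine taken alone, but here the CPK event is Grade 3. Nor is a two-marker rule foreign to the table: its ALT/AST rows already depend on bilirubin.

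A reader might also infer that such a patient is continued on both drugs without safeguard. The documents do not support that:

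- Section 7.413 requires the Study Chair to be contacted at once for any DLT. It states no hold, and it does not reach Cycle 1, later cycles or Phase II.
- Table 8.31 holds pembrolizumab for Grade 2 renal events and for other related Grade 3 events. Section 8.1 adjusts both agents when either may be the cause; this is most naturally read as applying each drug's own table. A looser reading could carry the renal hold to binimetinib, but the text does not say so.
- Section 15.198 asks for creatinine monitoring, and Section 10.61 requires CPK and creatinine to be graded at each evaluation. Section 8.1 adds: "All AEs should be followed weekly or as clinically appropriate until stabilization or resolution". This covers a creatinine rise once it is known, not its first detection between cycle visits.

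Finally, the count of 18 of 19 depends on relatedness to binimetinib. A DLT attributed to pembrolizumab alone draws no binimetinib action from the catch-all row.

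**Conclusion.** The point holds for binimetinib, the drug this row governs. A stated instruction gives the less cautious action for asymptomatic Grade 3 CPK with creatinine at or above 1.5 times screening, when the creatinine rise is Grade 1 or non-persistent Grade 2; at persistent Grade 2, action is optional. It is a narrow patient-safety gap, worth closing because closing it is cheap.

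The conclusion assumes that the DLT wording means a rise to at least 1.5 times screening, and that the events are at least possibly related. If the grading scale places every such rise at Grade 2 or above, the Grade 1 line is empty and the gap lies at Grade 2. The documents give no rate for the pair, so its frequency is unknown.

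A reader might infer that the dose-finding result is compromised. It is not: such a patient in Cycle 2 still counts as a DLT whatever is done with the dose, so DLT counting and the MTD are unaffected.

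**What to change.** **1. Grade 3 CPK row of Table 8.2.** Limit the maintain instruction to asymptomatic patients without an at least possibly related creatinine rise to 1.5 times screening or more. If such a rise is present, interrupt binimetinib until CPK is Grade 1 or lower and creatinine is below 1.5 times screening (or back to baseline). Then:

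- both resolved within 21 days: resume one dose level lower;
- CPK not resolved within 21 days: discontinue binimetinib, as the row already states for symptomatic patients;
- only creatinine unresolved: the investigator and Study Chair decide. Mandatory discontinuation here would be stricter than the discretionary resumption that the catch-all row allows after Grade 3 creatinine.

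The clinical team should confirm the action.

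**2. Weekly CK checks.** Add serum creatinine, read against screening, to the Grade 1-2 and Grade 3 CPK rows and to footnote 4 of Section 4.1.

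**Cost.** One condition in one row, and one analyte added to checks already ordered. Some patients will have an extra interruption or dose reduction, including some whose creatinine is still within normal limits because their screening value was low. The DLT definition, DLT counting and MTD rules stay as they are.
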